### SUMMARY OF CHANGES FROM PREVIOUS VERSION

Affected Section(s)	Summary of Revisions Made	Rationale
	N/A	First Emission

MENARINI	Corporate Medical Department		
	Pi	otocol Template	
Identification Number	Version Number	State	Effective date
FORM-000050125	2.0, CURRENT	Effective	08 Jan, 2021

Study Code: MEIN/21/AmNe-Hyp/001

### LIST OF ABBREVIATIONS AND DEFINITION OF TERMS

ABBREVIATION	DEFINITION
ADR	Adverse drug reaction
AE	Adverse event
AEOSI	Adverse event of special interest
ALT	Alanine aminotransferase
AST	Aspartate aminotransferase
AML	Amlodipine
ATC	Anatomical Therapeutic Chemical
BBs	Beta-Blockers
BP	Blood Pressure
CCBs	Calcium Channel Blockers
COVID-19	Coronavirus Disease 2019
CRO	Clinical Research Organization
CVD	Cardiovascular disease
DBP	Diastolic Blood Pressure
DPO	Data Protection Officer
EC	Ethics Committee
ECG	Electrocardiogram
EOT	End of Treatment
eCRF	Electronic Case Report Form
ESC	European Society of Cardiology
ESH	European Society of Hypertension
FPI	First Patient In
FSH	Follicular Stimulating Hormone
GCP	Good Clinical Practice
GLM	General linear model
HA	Health Authorities
HRT	Hormonal replacement therapy
ICF	Informed Consent Form
ICH	International Conference of Harmonisation
ICSR	Individual Case Safety Report
IMP	Investigational medicinal product
IP	Investigational product
IT	Information technology

CONFIDENTIAL

MENARINI	Corporate Medical Department		
	Р	rotocol Template	
Identification Number	Version Number	State	Effective date
FORM-000050125	2.0, CURRENT	Effective	08 Jan, 2021

IUD	Intrauterine Device
IUS	Intrauterine hormone-releasing system
LPO	Last Patient Out
mITT	Modified Intent-to-treat
NEB	Nebivolol
NO	nitric oxide
PI	Principal Investigator
PP	Protocol Population
RCT	Randomized controlled trial
SAE	Serious Adverse Events
SAP	Statistical Analysis Plan
SBP	Systolic Blood Pressure
SD	Standard deviation
SmPC	Summary of product characteristics
SOP	Standard Operative Procedures
SUSAR	Serious Unexpected Adverse Drug Reaction
TMF	Trial Master File
UPT	Urine pregnancy test
ULN	Upper Limit of Normal
WOCBP	Woman of Childbearing Potential

MENARINI	Corporate Medical Department		
	P	rotocol Template	
Identification Number	Version Number	State	Effective date
FORM-000050125	2.0, CURRENT	Effective	08 Jan, 2021

Study Code: MEIN/21/AmNe-Hyp/001

## 2 PROTOCOL SYNOPSIS

Title	Open-laBel, multicenter, multinatiOnal, inTerventional clinical Trial to assess effIcacy and safety of the extemporaneous Combination of nEbivoLol and amLodipine in grade 1-2 hypertensive patIents versus each monotherapy	
Acronym	BOTTICELLI Study	
Sponsor Study Code	MEIN/21/AmNe-Hyp/001	
Study product, Dosage and Regimen: - Investigational Product - Reference Therapy	Extemporaneous combination of nebivolol (NEB) 5 mg tablets (Anatomical Therapeutic Chemical [ATC] code: C07AB12) with	
(comparator)	Each monotherapy: NEB 5 mg and amlodipine (as besylate) 5 mg tablets	
Study Type and Design	This is a Phase IV, interventional, open-label, multicenter, multinational study with 2 study periods (a run-in period of 4 weeks and an assessment period of 8 weeks).	
	Screening Visit 1 (Week -4): Patients with Grade 1 - 2 hypertension with systolic blood pressure (SBP) ranging from $\geq 140$ to $\leq 179$ mmHg and diastolic blood pressure (DBP) ranging from $\geq 90$ to $\leq 109$ mmHg on treatment with any beta-blockers (BBs) or calcium channel blockers (CCBs) c including NEB 5 mg or AML 5 mg for at least one month prior to Visit 1 will be screened for eligibility.	
	Run-in period from Visit 1 (Week -4) to Visit 2 (Week 0) : On the same day of the Screening visit, eligible patients will enter into a run-in period after screening, during which:	
	
 
Patients receiving NEB 5 mg or AML 5 mg will continue the same therapy for 4 weeks.
 
Patients on any other BBs or CCBsc will be switched to NEB 5 mg or AML 5 mg.
 
	

MENARINI	Corporate Medical Department		
	Р	rotocol Template	
Identification Number	Version Number	State	Effective date
FORM-000050125	2.0, CURRENT	Effective	08 Jan, 2021

	Patients entering this phase in therapy with NEB 5 mg or AML 5 mg should be in a 1:1 ratio.
	Assessment period from Visit 2 (Week 0) to Visit 4 (Week 8): After 4 weeks ( $\pm 2$ days) of run-in period of monotherapy, BP will be further assessed at Visit 2. Patients with uncontrolled BP levels (sitting SBP/DBP $\geq$ 130/80 mmHg) at Visit 2, with the treatment adherence (ranging between 80% to 120%) who did tolerate the treatment will enter into the assessment period and will be assigned to the extemporaneous combination of NEB 5 mg and AML 5 mg. Patients with controlled BP levels (sitting SBP/DBP <130/80 mmHg) and/or who do not tolerate the treatment or have an adherence range below 80% or above 120%, will be withdrawn from the study.
	After 4 weeks ±2 days in the assessment period, patients BP will be further evaluated at Visit 3: patients with controlled BP levels (sitting SBP/DBP <130/80 mmHg) will continue the same extemporaneous combination, while patients with uncontrolled BP levels will be uptitrated from extemporaneous combination NEB/AML 5/5 mg to extemporaneous combination of NEB/AML 5/10 mg for further 4 weeks.
	At the end of the assessment period (8 weeks $\pm 4$ days), Visit 4 will take place. To correctly evaluate the additional effect of the combination therapy, the number of patients with uncontrolled BP on NEB or AML monotherapy needs to be balanced at Visit 2. In order to maintain a 1:1 ratio during the assessment period, a cap of 110 patients for each treatment arm (ie. NEB and AML) will be included at Visit 2 in order to maintain a balanced number of uncontrolled patients entering the assessment period for each drug. The evaluation will be done every 50 patients. If the rate of entrance in the assessment period for one of the 2 tested drugs will deviate more than 5%, a corrective measure will be initiated: according to the enrolment site statistics, one or more sites will be informed to enroll a greater number of patients being treated with the least represented drug in the assessment period.

MENARINI	Corporate Medical Department		
	Р	rotocol Template	
Identification Number	Version Number	State	Effective date
FORM-000050125	2.0, CURRENT	Effective	08 Jan, 2021

Phase	A total number of 290 patients will be screened considering 25% of drop-out rate, to obtain approximately 216 completed patients at the end of the study (Visit 4). IV
Objectives	Primary objective:
	
 
To assess the antihypertensive efficacy of the extemporaneous combination of NEB 5 mg with AML 5 mg or AML 10 mg in lowering the sitting DBP between Visit 2 (Week 0) and Visit 4 (Week 8) in patients with uncontrolled BP, previously treated with NEB 5 mg or AML 5 mg monotherapies for at least 4 weeks.
 

	Secondary objectives:

 
Secondary objectives:
 
To assess the antihypertensive efficace extemporaneous combination of NEB 5 mg with or AML 10 mg in lowering sitting SBP betweek 0) and Visit 4 (Week 8) in patients with BP previously treated with NEB 5 mg or monotherapies for at least 4 weeks.
 
To assess the antihypertensive efficace extemporaneous combination of NEB/AML 5/1 extemporaneous combination of NEB/AML lowering sitting DBP and SBP between Visit and Visit 4 (Week 8) in patients with uncomplete the set of the set of

	
	previously treated with NEB 5 mg or AML 5 mg
	monotherapies for at least 4 weeks.
	• To assess the antihypertensive efficacy of the extemporaneous combination of NEB 5 mg with AML 5 mg or AML 10 mg by evaluating the patients who achieve BP goal (sitting BP <130/80 mmHg) at Visit 2 (Week 0), at Visit 3 (Week 4), and at Visit 4 (Week 8).
	• To assess the compliance to the treatment (percentage of
	actual doses taken versus doses to be taken) at Visit 2 (Week 0), at Visit 3 (Week 4), and at Visit 4 (Week 8).
	• To evaluate the safety and tolerability of the monotherapies (NEB 5 mg and AML 5 mg) and of the extemporaneous

MENARINI	Corporate Medical Department				
	Protocol Template				
Identification Number	Version Number	State	Effective date		
FORM-000050125	2.0, CURRENT	Effective	08 Jan, 2021		

	combinations (NEB 5 mg and AML 5mg or AML 10 mg) after 8 weeks of treatment.
I	Exploratory objectives:
	
 
To assess change in mean sitting DBP and SBP between Visit 1 (Week -4) and Visit 2 (Week 0), Visit 3 (Week 4), and Visit 4 (Week 8):
 

	• In the group of patients who were on NEB 5 mg and AML 5 mg at Visit 1 and continued to be on the same therapies.
	
 
In the group of patients who switched to NEB 5 mg or AML 5 mg from any other BBs or CCBs at Visit 1.
 

	• To assess the change in mean sitting DBP and SBP between Visit 2 (Week 0) and Visit 3 (Week 4) for uncontrolled patients at Visit 3 (Week 4).
	• To assess the antihypertensive efficacy of the extemporaneous combination of NEB 5 mg with AML 5 mg or AML 10 mg by evaluating the number of patients achieving the BP goal (sitting BP <130/80 mmHg) at Visit 2 (Week 0), Visit 3 (Week 4) and Visit 4 (Week 8):
	
 
In the group of patients who were on NEB 5 mg and AML 5 mg at Visit 1 (Week -4) and continued to be on the same therapies.
 

	
 
In the group of patients who switched to NEB 5 mg or AML 5 mg from any other BBs or CCBs at Visit 1 (Week -4).
 

	• To assess the antihypertensive efficacy of the extemporaneous combination of NEB 5 mg with AML 5 mg or AML 10 mg by evaluating the number of patients divided into subgroups according to the hypertension grade, the presence of diabetes and/or of hypercholesterolemia achieving the BP goal (sitting BP <130/80 mmHg) at Visit 2 (Week 0), Visit 3 (Week 4), and Visit 4 (Week 8):
	
 
In the group of patients who were on NEB 5 mg and AML 5 mg at Visit 1 and continued to be on the same therapies.
 

MENARINI	Corporate Medical Department				
	Protocol Template				
Identification Number	Version Number	State	Effective date		
FORM-000050125	2.0, CURRENT	Effective	08 Jan, 2021		

	• In the group of patients, who switched to NEB 5 mg or AML 5 mg from any other BBs or CCBs at Visit 1.	
Endpoints	Primary endpoint:	
1	• Change in mean sitting DBP between Visit 2 (Week 0) and Visit 4 (Week 8).	
	Secondary endpoints:	
	• Change in mean sitting SBP between Visit 2 (Week 0) and Visit 4 (Week 8).	
	• Change in mean sitting DBP and SBP between Visit 3 (Week 4) and Visit 4 (Week 8) in patients receiving extemporaneous combination of NEB/AML 5/5 mg versus patients uptitrated to the extemporaneous combination of NEB/AML 5/10 mg.	
	• Number and proportion of patients achieving the BP goal (sitting SBP/DBP <130/80 mmHg) at Visit 2 (Week 0), Visit 3 (Week 4), and Visit 4 (Week 8).	
	• Adherence to the treatments (% of doses taken/doses to be taken) at Visit 2 (Week 0), Visit 3 (Week 4), and Visit 4 (Week 8).	
	
 
Safety and tolerability of the monotherapies (NEB 5 mg and AML 5 mg) and of the extemporaneous combinations (NEB 5 mg and AML 5 mg or AML 10 mg) will be measured by incidence, intensity (severity), seriousness of Adverse Events during the study period, (screening, run-in period and assessment period), relationship to the study treatments, Adverse events of special interest, clinically significant abnormal change in vital signs, electrocardiogram (only at Visit 1 and Visit 4), laboratory parameters (if applicable) at Visit 2 (Week 0), Visit 3 (Week 4), and Visit 4 (Week 8).
 
	
	Exploratory Endpoints:	
	• Change in mean sitting DBP and SBP between Visit (Week -4) and Visit 2 (Week 0), Visit 3 (Week 4) an Visit 4 (Week 8):	
	• In the group of patients who were on NEB 5 mg and	

MENARINI	Corporate Medical Department				
	Protocol Template				
Identification Number	Version Number	State	Effective date		
FORM-000050125	2.0, CURRENT	Effective	08 Jan, 2021		

	AML 5 mg at Visit 1 and continued to be on the
	
 
same therapies.
 
In the group of patients who switched to NEB 5 mg or AML 5 mg from any other BBs or CCBs at Visit 1.
 

	
 
Change in mean sitting DBP and SBP for uncontrolled patients at Visit 3 (Week 4), between Visit 2 (Week 0) and Visit 3 (Week 4).
 
Number and proportion of patients achieving the BP goal (sitting SBP/DBP <130/80 mmHg) at Visit 2 (Week 0), Visit 3 (Week 4), and Visit 4 (Week 8): 
 
In the group of patients who were on NEB 5 mg and AML 5 mg at Visit 1 (Week -4) and continued to be on the same therapies.
 
 
 

	
 
In the group of patients who switched to NEB 5 mg or AML 5 mg from any other BBs or CCBs at Visit 1 (Week- 4).
 

	• Number and proportion of patients divided into subgroups according to the hypertension grade, the presence of diabetes and/or of hypercholesterolemia achieving the BP goal (sitting SBP/DBP <130/80 mmHg) at Visit 2 (Week 0), Visit 3 (Week 4), and Visit 4 (Week 8):
	
 
In the group of patients who were on NEB 5 mg and AML 5 mg at Visit 1 (Week -4) and continued to be on the same therapies.
 

	
 
In the group of patients, who switched to NEB 5 mg or AML 5 mg from any other BBs or CCBs at Visit 1 (Week -4).
 

Study Population: Patients characteristics Number of Patients	Approximately 290 male or female uncontrolled hypertensive patients between $\geq 18$ and $< 65$ years of age, who are on treatment with any BBs or CCBs, including NEB (only 5 mg dosage allowed) or AML (only 5 mg dosage allowed) for at least one month prior to
	Visit 1, will be screened for eligibility. A total number of 290 patients will be screened considering a screen failure/drop-out rate of 25%, to obtain approximately 216 completed patients at the end of the study (Visit 4).

MENARINI	Corporate Medical Department				
	Protocol Template				
Identification Number	Version Number	State	Effective date		
FORM-000050125	2.0, CURRENT	Effective	08 Jan, 2021		

Inclusion criteria:
A patient will be considered eligible to be enrolled in the study only if he/she meets all the following inclusion criteria:

 
Male or female patients with Grade 1 - 2 hypertension with mean sitting SBP ≥140 mmHg and ≤179 mmHg and/or mean sitting DBP ≥90 mmHg and ≤109 mmHg at screening (in accordance with the 2018 European Society of Cardiology / European Society of Hypertension guidelines definition), ≥18 and <65 years of age, on monotherapy treatment either with BBs or CCBs for at least 4 weeks before Visit 1 (screening).
 
Patients are able to understand and have freely given written informed consent at Screening Visit.
 
Patients who are able to comply with all study procedures and who are available for the duration of the study.
 
Ability to take oral medication and willing to adhere to the drug regimen.
 
Female patients are eligible to participate if not pregnant, or not breastfeeding and if they refrain from donating or storing eggs. For females of reproductive potential: use of highly effective contraception (eg. method of birth control throughout the study period and for 4 weeks after study completion defined as a method which results in a failure rate of <1% per year) such as:         
 
Combined hormonal contraception (estrogen- and progestogen-containing) associated with inhibition of ovulation (oral, intravaginal, and transdermal).
 
Progestogen-only hormonal contraception associated with inhibition of ovulation (oral, injectable, and implantable).
 
 
 

 
Intrauterine device.
 

• Intrauterine hormone-releasing system.
• Bilateral tubal occlusion.
• Vasectomized partner (procedure conducted at least
2 months before the screening), (provided the

MENARINI	Corporate Medical Department				
	Protocol Template				
Identification Number	Version Number	State	Effective date		
FORM-000050125	2.0, CURRENT	Effective	08 Jan, 2021		

	6.	partner is the sole sexual partner of the trial participant and that the vasectomized partner has received medical assessment of the surgical success). A male patient must agree to use contraception during the whole study period and for at least 1 week after the last dose of study treatment and refrain from donating sperms during this period.
Ε	xclus	ion criteria:
	• •	tient who meets any of the following criteria will not qualify ry into the study:
		Patients with significant history of hypersensitivity to nebivolol, amlodipine, other BBs or other dihydropyridines, or any related products (including excipients of the formulations) as outlined in the relevant Investigators Brochures, summary of product characteristics  or local package inserts for NEB and AML. Patients with serious disorders (in the opinion of the Investigator) which may limit the ability to evaluate the efficacy or safety of the tested medications, including cerebrovascular, cardiovascular, renal, respiratory, hepatic, gastrointestinal, endocrine or metabolic, hematological, or oncological, neurological, and psychiatric diseases. The same applies for immunocompromised and/or neutropenic patients.
	3.	Patients having a history of the following conditions within the last 6 months: myocardial infarction, unstable angina pectoris, percutaneous coronary intervention, bypass surgery, heart failure, hypertensive encephalopathy, valve replacement (transcatheter aortic valve implantation, mitraclip), cerebrovascular accident (stroke), or transient ischemic attack.
	4.	Patients with condition of hypotension with SBP <90 mmHg and/or DBP <60mmHg.
	5.	Acute heart failure, cardiogenic shock, or episodes of heart failure decompensation requiring intravenous inotropic

MENARINI	Corporate Medical Department				
	Protocol Template				
Identification Number	Version Number	State	Effective date		
FORM-000050125	2.0, CURRENT	Effective	08 Jan, 2021		
-					

	
 
therapy.
 
6. Patients with secondary hypertension of any etiology including renal diseases, pheochromocytoma, Cushing's syndrome, hyperaldosteronism, renovascular disease, and thyroid disorders.
 
7. Patients with a narrowing of the aortic or bicuspid valve, an obstruction of cardiac outflow (obstructive, hypertrophic cardiomyopathy), obstruction of the outflow tract of the left ventricle (eg. high grade aortic stenosis) or symptomatic coronary disease.
 

	
 
8. Patients with severe renal impairment or renal transplant.
 
9. Patients with clinically relevant hepatic impairment.
 

	10. Patients with sick sinus syndrome, including sino-atrial block.
	11. Patients with second- or third-degree heart block (without a pacemaker).
	12. Patients with history of bronchospasm and bronchial asthma.
	13. Patients with untreated pheochromocytoma.
	14. Patients with bradycardia (heart rate <60 bpm; <50 bpm in patients already on BBs treatment).
	

15. Patient with metabolic acidosis.

16. Patients with severe peripheral circulatory disturbances.

	
 
17. Participation in another interventional study within the last
 
4 weeks before Screening Visit (Visit 1).
 

	18. Patients with diseases that, in the opinion of the Investigator, prevent a careful adherence to the protocol.
	19. Patients using and not suitable for withdrawing the
	prohibited medications prior to the administration of study treatment.
Clinical Sites	Approximately 25 investigational clinical sites
Number of Centers	
List of Countries	Bulgaria, Poland, and Ukraine.
Study Duration (specify different study phases):	This study will last 12 weeks.
annerent study phases).	Screening Visit (Visit 1, Week -4):

MENARINI	Corporate Medical Department		
	Р	Protocol Template	
Identification Number	Version Number	State	Effective date
FORM-000050125	2.0, CURRENT	Effective	08 Jan, 2021

Study Code: MEIN/21/AmNe-Hyp/001

	Grade 1 - 2 hypertensive patients (BP ranging from ≥140 to			
	$\leq$ 179mmHg for SBP and from $\geq$ 90 to $\leq$ 109 mmHg for DBP) on			
	treatment with any BBs or CCBs c , including NEB (only 5 mg			
	dosage allowed) or AML (only 5 mg dosage allowed) for at least one month prior to Visit 1 will be screened for eligibility.			
	one month prior to visit i will be screened for englointy.			
	Run-in period (4 weeks) from Visit 1 (Week -4) to Visit 2			
	$\frac{(\text{Week } 0)}{(1 + 1)}$			

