## 6.2 Inclusion and Exclusion Criteria

A patient will be considered eligible to be enrolled in the study only if he/she meets all of the inclusion criteria and none of the exclusion criteria.

MENARINI	Corporate Medical Department Protocol Template		nent
Identification Number	Version Number	State	Effective date
FORM-000050125	2.0, CURRENT	Effective	08 Jan, 2021

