### *Study Code:* MEIN/21/AmNe-Hyp/001

### 6.2.1 Inclusion Criteria

A patient will be considered eligible for inclusion in the study only if all of the following criteria are met:

- 1. Male or female patients with Grade 1 2 hypertension with mean sitting SBP ≥140 mmHg and ≤179 mmHg and/or mean sitting DBP ≥90 mmHg and ≤109 mmHg at screening (in accordance with the 2018 ESC/ESH guidelines definition), ≥18 and <65 years of age, on monotherapy treatment either with BBs or CCBs for at least 4 weeks before Visit 1 (screening).
- 2. Patients are able to understand and have freely given written informed consent at Screening Visit.
- 3. Patients who are able to comply with all study procedures and who are available for the duration of the study.
- 4. Ability to take oral medication and willing to adhere to the drug regimen.
- 5. Female patients are eligible to participate if not pregnant, or not breastfeeding and if they refrain from donating or storing eggs. For females of reproductive potential: use of highly effective contraception (eg. method of birth control throughout the study period and for 4 weeks after study completion defined as a method which results in a failure rate of <1% per year) such as:
  - Combined hormonal contraception (estrogen- and progestogen-containing) associated with inhibition of ovulation (oral, intravaginal, and transdermal).
  - Progestogen-only hormonal contraception associated with inhibition of ovulation (oral, injectable, and implantable).
  - Intrauterine device.
  - Intrauterine hormone-releasing system.
  - Bilateral tubal occlusion.
  - Vasectomized partner (procedure conducted at least 2 months before the screening), (provided the partner is the sole sexual partner of the trial patient and that the vasectomized partner has received medical assessment of the surgical success).
- 6. A male patient must agree to use contraception during the whole study period and for at least 1 week after the last dose of study treatment and refrain from donating sperms during this period.

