### 6.2.2 Exclusion Criteria

Any patient who meets any of the following criteria will not qualify for entry into the study:

MENARINI	Corp	porate Medical Departme	ent
	Protocol Template		
Identification Number	Version Number	State	Effective date
FORM-000050125	2.0, CURRENT	Effective	08 Jan, 2021

Study Code: MEIN/21/AmNe-Hyp/001

- 1. Significant history of hypersensitivity to nebivolol, amlodipine, other BBs or other dihydropyridines, or any related products (including excipients of the formulations)as outlined in the relevant Investigators Brochures, summary of product characteristics (SmPC) or local package inserts for NEB and AML.
- 2. Patients with serious disorders (in the opinion of the Investigator) which may limit the ability to evaluate the efficacy or safety of the tested medications, including cerebrovascular, cardiovascular, renal, respiratory, hepatic, gastrointestinal, endocrine/or metabolic, hematological, or oncological, neurological, and psychiatric diseases. The same applies for immunocompromised and/or neutropenic patients.
- 3. Patients having a history of the following conditions within the last 6 months: myocardial infarction, unstable angina pectoris, percutaneous coronary intervention, bypass surgery, heart failure, hypertensive encephalopathy, valve replacement (transcatheter aortic valve implantation, mitraclip), cerebrovascular accident (stroke), or transient ischemic attack.
- 4. Patients with condition of hypotension with SBP <90 mmHg and/or DBP <60mmHg.
- 5. Acute heart failure, cardiogenic shock or episodes of heart failure decompensation requiring intravenous inotropic therapy.
- 6. Patients with secondary hypertension of any etiology including renal diseases, pheochromocytoma, Cushing's syndrome, hyperaldosteronism, renovascular disease, thyroid disorders.
- 7. Patients with a narrowing of the aortic or bicuspid valve, an obstruction of cardiac outflow (obstructive, hypertrophic cardiomyopathy), obstruction of the outflow tract of the left ventricle (eg. high grade aortic stenosis) or symptomatic coronary disease.
- 8. Patients with severe renal impairment or renal transplant.
- 9. Patients with clinically relevant hepatic impairment.
- 10. Patients with sick sinus syndrome, including sino-atrial block.
- 11. Patients with second- or third-degree heart block (without a pacemaker).
- 12. Patients with history of bronchospasm and bronchial asthma.
- 13. Patients with untreated pheochromocytoma.

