### 8.2.5 Urine Pregnancy tests

Urine pregnancy tests (when appropriate) will be performed at Visit 1, 2, 3, and 4, by determination of the urine  $\beta$  human chorionic gonadotropine, using locally available commercial dipsticks. Unscheduled re-tests can be performed as required according to the Investigator's judgment.

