### 9.13 Management of pregnancy exposure cases

The Investigator is expected to record in the provided form any case of pregnancy exposure occurring in a female patient or in a male patient's partner the treatment and follow-up periods, sending it within 5 days after being made aware of the pregnancy, to the CRO by e-mail or fax, to be forwarded to the Sponsor.

The Investigator is requested to follow each case of pregnancy exposure until the outcome.

If the pregnancy results in an abnormal outcome, this will be recorded in the eCRF as a SAE and managed as above described.

Eligibility of a woman of childbearing potential (WOCBP) will be considered as described in Section 6.2.1. A woman is considered fertile following menarche and until becoming postmenopausal unless permanently sterile as described below.

MENARINI	Corporate Medical Department		ent
	Р	rotocol Template	
Identification Number	Version Number	State	Effective date
FORM-000050125	2.0, CURRENT	Effective	08 Jan, 2021

*Study Code:* MEIN/21/AmNe-Hyp/001

Women in the following categories are not considered WOCBP if:

- Premenarchal
- Premenopausal female with one of the following:
  - Documented hysterectomy.
  - Documented bilateral salpingectomy.
  - Documented bilateral oophorectomy.

Note: Documentation can come from the study site personnel's review of the patient's medical records, medical examination, or medical history interview.

• Postmenopausal female: A postmenopausal state is defined as no menses for 12 months without an alternative medical cause. A high follicle stimulating hormone (FSH) level to 30 mIU/mL or higher may be used to confirm a postmenopausal state in women not using hormonal contraception or hormonal replacement therapy (HRT). However, in the absence of 12 months of amenorrhea, a single FSH measurement is insufficient. Females on HRT and whose menopausal status is in doubt will be required to use one of the non-estrogen hormonal highly effective contraception methods if they wish to continue their HRT during the study. Otherwise, they must discontinue HRT to allow confirmation of postmenopausal status before study enrolment.

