### Withdrawal of patient from the study

The patient may withdraw from the study at any time without explanation, without losing the right to future medical care. The participation of the patient may, at any moment, be terminated by the Investigator, if considered appropriate.

A patient can be withdrawn during the study for any of the following reasons:

- Any AE, which required treatment and study termination for the patient according to the Investigator's judgment.
- Abnormal renal function or liver enzyme parameters as described in Section 8.2.3.
- Patient becomes pregnant during the study.
- Request of the patient (without giving any reason).
- Investigator deems it to be in the best interest of the patient to discontinue.
- Failure to adequately comply with the dosing, evaluations, or other requirements of the study.
- If the patient meets an exclusion criterion (newly developed or not previously recognized) that precludes further study participation.
- Use of any prohibited medication that in the opinion of the Investigator or Sponsor necessitates the patient being withdrawn.

The reason for the withdrawal of study treatment, or withdrawal from the study must be well documented in the source documents and in the eCRF page and should capture the date and the specific underlying reason for discontinuation of study treatment or patient discontinuation/withdrawal.

MENARINI	Corporate Medical Department		
	Р	Protocol Template	
Identification Number	Version Number	State	Effective date
FORM-000050125	2.0, CURRENT	Effective	08 Jan, 2021

*Study Code:* MEIN/21/AmNe-Hyp/001

Patients who discontinue from the study early will be asked, anyway, to complete all the assessments of Visit 4. Patients may discontinue the study treatment, but remain in the study for follow-up, especially for safety study endpoints (if applicable).

If a patient has been discontinued/withdrawn due to an AE, the Investigator must immediately notify the relevant pharmacovigilance contact (see Section 9.9) and should be followed-up until the AE is resolved or the Investigator deems further observations or examinations as no longer medically indicated.

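### Inclusion criterion 5 joins the pregnancy and breastfeeding conditions with 'or', so read literally it bars only a woman who is both, and for breastfeeding no other provision fills the gap

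*Protocol*

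**What the plan says.** Criterion 5 appears twice, in the Protocol synopsis (inclusion criteria) and in Section 6.2.1. Both copies read: "Female patients are eligible to participate if not pregnant, or not breastfeeding and if they refrain from donating or storing eggs". Section 6.2 makes a patient eligible only if he or she "meets all of the inclusion criteria and none of the exclusion criteria", and Section 6.2.2 opens its list of 19 exclusions with "Any patient who meets any of the following criteria will not qualify for entry into the study".

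The other provisions that bear on the point are:

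- **Contraception**, within criterion 5 itself: "For females of reproductive potential: use of highly effective contraception".
- **Testing**, Section 8.2.5: "Urine pregnancy tests (when appropriate) will be performed at Visit 1, 2, 3, and 4". Section 5.1 places the Visit 1 urine test among the procedures to be finished on the screening day before the run-in starts.
- **Women of childbearing potential**, Section 9.13: "Eligibility of a woman of childbearing potential (WOCBP) will be considered as described in" Section 6.2.1. The same section sets out the reporting and follow-up of pregnancy exposure.
- **Withdrawal**, Section 10, where one listed reason is: "Patient becomes pregnant during the study".

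**The concern.** An inclusion criterion is applied as written, here at about 25 sites in three countries and to women from 18 to under 65 years of age. With 'or', a pregnant woman who is not breastfeeding meets the second condition, and a breastfeeding woman who is not pregnant meets the first. Each then satisfies the sentence that appears intended to keep her out. Eligible patients start the run-in and receive study medication on the day of screening, which leaves little time to catch a misreading.

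What is at stake is the clarity of a safety rule at entry. No estimate, error rate or sample size depends on it.

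**Working it through.** No figure in the plan applies here, so the check is one of logic and cross-reading.

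**Step 1. The sentence as written.** Let P be pregnant, B breastfeeding and R refrains from donating or storing eggs. For a woman with R true:

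| P | B | 'not P or not B' (as written) | 'not P and not B' (evident purpose) |
|---|---|---|---|
| no | no | passes | passes |
| yes | no | passes | barred |
| no | yes | passes | barred |
| yes | yes | barred | barred |

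As written, 3 of 4 combinations pass; the evident purpose admits 1 of 4. These are cells of a logic table and say nothing about how many patients fall in each.

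**Step 2. Does the grouping of 'or' and 'and' matter?** The sentence can be read as (not P or not B) and R, or as not P or (not B and R). With R true, both reduce to 'not P or not B', so the table stands. The grouping changes the result only for a woman who does not refrain.

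**Step 3. Does the second copy correct the first?** No. The synopsis and Section 6.2.1 carry the same words, and Section 9.13 sends eligibility of women of childbearing potential back to Section 6.2.1.

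**Step 4. Do the exclusion criteria close the gap?** Of the 19 criteria, 0 name pregnancy, breastfeeding or lactation, in the synopsis or in Section 6.2.2. Criterion 1 cites the product characteristics for hypersensitivity only. Criteria 2 and 18 concern disorders and diseases.

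**Step 5. What do the other provisions cover?**

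| Provision | Pregnancy at entry | Breastfeeding at entry |
|---|---|---|
| Contraception (criterion 5) | supports 'not pregnant', but does not address a current pregnancy | not addressed |
| Visit 1 urine test (Sections 5.1, 8.2.5) | detects it before run-in; no text states what a positive result means for entry | not addressed |
| Withdrawal (Section 10) | names a pregnancy arising during the study | not addressed |
| Exposure reporting (Section 9.13) | covers reporting and follow-up, not entry | not addressed |

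Section 10 also allows withdrawal for a condition not recognised earlier, but only where that condition is an exclusion criterion, and by Step 4 neither condition is one.

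**The case against.** The strongest reply is that nobody would apply the sentence literally. A rule that stopped only women who were pregnant and breastfeeding at once would serve no purpose, and 'not X, or not Y' is a common loose way of writing 'neither'. For pregnancy the surrounding text agrees: a urine test that must be done before the run-in has little use except to apply the 'not pregnant' condition, contraception is required, and the test is repeated at Visits 2, 3 and 4. This stands as evidence of intent and is why the point is minor. It does not repair the sentence, and it does not help with breastfeeding.

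A reader might also infer three stronger things that the documents do not support.

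- **That trial entry is what first exposes a fetus or nursing infant.** Criterion 1 requires beta-blocker or calcium channel blocker monotherapy for at least 4 weeks before Visit 1. Entry continues that treatment or switches it to nebivolol or amlodipine. The second drug is added from Visit 2, where another urine test is scheduled.
- **That such an enrolment could not be called a protocol deviation.** SAP Section 9.2 has all deviations reviewed case by case before database lock, and nothing ties that review to the literal grammar of a criterion. The investigator may also end participation at any time under Section 10.
- **That a negative urine test must be written in as an entry condition.** That would be a new eligibility rule, going beyond a drafting error in the existing one.

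**Conclusion.** The point holds as a minor wording error in an operative safety criterion. Read literally, criterion 5 bars 1 of 4 combinations where its evident purpose is to bar 3, and no exclusion criterion makes up the difference. For pregnancy, other provisions show the intent and reduce the practical risk. For breastfeeding, criterion 5 is the only text, so the gap there has no other cover.

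The conclusion assumes that 'neither' is what the sponsor meant, which the rest of the protocol supports for pregnancy and common sense supports for breastfeeding. It also rests on the protocol and SAP alone, since the consent pages were not available. How many women could be affected cannot be derived from the documents. The sample size, analysis methods and error rates do not change.

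**What to change.** In the synopsis and in Section 6.2.1, reword criterion 5 so that a female patient must be not pregnant **and** not breastfeeding, in line with the criterion's own evident purpose. At the same time, read it against the Visit 1 procedures (Section 5.1), pregnancy testing (Section 8.2.5), pregnancy exposure (Section 9.13) and withdrawal (Section 10), and reconcile them so that all describe the same rule. Do not add a test-based entry condition as part of this correction.

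The cost is one word in two places plus the amendment or notification step in Protocol Section 12.6. No procedure, visit or analysis is added.
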